9.3.2. Analysis of the Secondary Endpoint(s)

Improvement in SF-36, EQ-5D, ODI, and VAS scores will be compared between groups using a repeated measure ANOVA (analysis of variance).

The occurrence rate of adverse events will be assessed using a Kaplan-Meier approach and a comparison of serious adverse event rates will be made using a chi-squared analysis.

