3.2. Secondary Objective(s)

The secondary objectives of this study are to:

- Compare participants' pre-surgical and post-surgical VAS, ODI, EQ-5D, and SF-36 scores to determine whether treatment with Tritanium or PEEK yields faster pain and quality of life improvement.
- Monitor device safety by gathering adverse event reports

4. Study Design and Endpoints

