4.2.2. Secondary Endpoint(s)

The secondary endpoints are:

- Improvement in lower-back and leg pain VAS score at follow-up visits
- Improvement in ODI at follow-up visits
- Improvement in Quality of Life as measured by the SF-36 and EQ-5D at follow-up visits
- Serious adverse events
- Proportion of participants using narcotics
- Proportion of participants returning to work
- Proportion of participants relying on assistive ambulatory device
- Proportion of participants requiring revision/secondary surgical intervention

5. Study Enrollment and Withdrawal

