5.3. Strategies for Recruitment and Retention

20 participants will be recruited for this study, and it is anticipated that 30 patients will need to be screened in order to reach the target enrollment. There is an anticipated accrual rate of 2 participants per month. Participants will be recruited from the office of Neurosurgery Consultants. The study synopsis will be provided on Riverside's research website; no other forms of advertisement are planned.

Due to the long-term participation involved in this research study, participants will be contacted and provided with visit reminders when their visit date is approaching. In addition, to incentivize attending follow-up visits, participants will be compensated \$25 per study visit in the form of a check.

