6.3. Study Schedule

6.3.1. Screening/Enrollment/Baseline Visit

Patients will be screened against inclusion and exclusion criteria at conventional care visits. The patient's signature must be obtained on the informed consent form before performing any assessment that goes beyond the standard of care. A subject is enrolled in the study when the ICF is signed and the PI has determined that the subject meets all eligibility criteria.

Enrollment/Baseline Visit (Visit 1)

- Obtain informed consent of potential participant verified by signature on study informed consent form
- Review medical history to determine eligibility based on inclusion/exclusion criteria.
- Review medications history to determine eligibility based on inclusion/exclusion criteria.
- Perform medical examinations needed to determine eligibility based on inclusion/exclusion criteria.
- Provide participants with instructions on CT and X-ray follow-up schedule
- Obtain urine pregnancy test for women of child-bearing age who have not had a hysterectomy/or sterilization
- Obtain demographic information, medical history, medication history, diabetes status, chronic steroid use, and alcohol and tobacco use history
- Record vital signs, results of examinations, other assessments
- Obtain participant's responses on VAS, ODI, EQ-5D, SF-36, and Press Ganey Patient Satisfaction Scale.
- Explain study follow-up schedule.
- Schedule x-ray with flexion and extension

 Schedule surgical procedure for participants who are eligible and available for the duration of the study.

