9.2. Statistical Hypotheses

Primary Efficacy Endpoint(s):

Spinal Fusion

- Alternative Hypothesis: Implanting the Tritanium posterior lumbar cage results in satisfactory spinal fusion time in patients aged ≥ 21 years with degenerative disk disease and undergoing a spinal fusion in a one level or two contiguous levels from L2 to S1 compared to those who received PEEK implant as measured over a 6-week, 3-month, 6-month and 12month post-operative period
- Null Hypothesis: Implanting the Tritanium posterior lumbar cage does not result in an satisfactory spinal fusion time in patients aged ≥ 21 years with degenerative disk disease and undergoing a spinal fusion in a one level or two contiguous levels from L2 to S1 compared to those who received PEEK implant as measured over a 6-week, 3-month, 6-month and 12-month post-operative period

Secondary Efficacy Endpoints(s):

Questionnaires

- Alternative Hypothesis: Participants implanted with the Tritanium posterior lumbar cage
 will report higher quality of life improvement, pain improvement, and disability
 improvement scores compared to participants implanted with the PEEK AVS uniLIF Spacer
 System as measured over a 6-week, 3-month, 6-month and 12-month post-operative period
- **Null Hypothesis:** There will be no difference between the quality of life, pain, and disability scores in participants that were implanted with the Tritanium or PEEK AVS uniLIF Spacer System as measured over a 6-week, 3-month, 6-month and 12-month post-operative period

Adverse Events

- Alternative Hypothesis: There will be a difference in the number and severity of adverse
 events observed between participants who were implanted with the Tritanium posterior
 lumbar cage compared to participants who were implanted with the PEEK AVS uniLIF Spacer
 System as measured over a 6-week, 3-month, 6-month and 12-month post-operative period
- **Null Hypothesis:** There will be no difference in the number and severity of adverse events observed between participants who were implanted with the Tritanium posterior lumbar cage compared to participants who were implanted with the PEEK AVS uniLIF Spacer System as measured over a 6-week, 3-month, 6-month and 12-month post-operative period

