9.3.3. Baseline Descriptive Statistics

Descriptive statistics of all participants enrolled will be generated, including demographics and clinical diagnosis characteristics at baseline.

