9.4. Measures to Minimize Bias

9.4.1. Enrollment/Randomization/Masking Procedures

Study participants will be assigned to study groups by permuted block random assignment at the enrollment visit after a study investigator has determined that the participant meets all inclusion criteria and no exclusion criteria. The study participants will be blinded to which group they have been assigned.

One potential bias that has been identified is the impact of knowing which device one has received on subsequent rating scales. Participants who are aware that they have been implanted with the Tritanium PL Cage may be more inclined to rate their pain as "improved." To ensure participant survey responses are not confounded, participants will blinded to which study group he or she is assigned.

Trial randomization codes will be tracked by the research coordinator by marking the designated section on study participants' enrollment visit CRF. Planned unmasking will occur at the final study visit (12-month visit). Unplanned masking is defined as unmasking that occurs before the final study visit. If a study participant learns to which group he or she was assigned, it will be noted on his or her case report form that masking has been broken. The participant is still permitted to participate in the research study.

Another potential bias that has been identified is the radiologists' interpretation of the CT and X-ray scans. Radiologists who are not informed of the study's hypotheses will perform CT and X-ray evaluation to avoid bias in the interpretation of fusion rate. In addition, two radiologists will independently evaluate the fusion following the guidelines described in this protocol to establish inter-rater reliability.

No dummy techniques will be necessary, as patients will be unable to determine with which device they're implanted. Epic will be utilized to inform other health care providers that the implanted device should not be revealed to the participant.

Study participants who discontinue early (at or before the 6-week study visit) may be replaced if the radiographic imaging was not performed.

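### The questionnaire comparisons name no baseline covariate; adding each participant's baseline score would remove the effect of chance imbalance and usually gain precision

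*Protocol*

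**What the plan says.** Protocol 9.3.2 gives one sentence on the four questionnaires: "Improvement in SF-36, EQ-5D, ODI, and VAS scores will be compared between groups using a repeated measure ANOVA (analysis of variance". No covariate is named there or elsewhere in section 9.

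The endpoint is worded as improvement, for example "Improvement in ODI at follow-up visits" in 4.2.2. Section 3.2 gives the reference point: "Compare participants' pre-surgical and post-surgical VAS, ODI, EQ-5D, and SF-36 scores". Improvement is therefore naturally read as change from the pre-surgical score, although 9.3.2 does not say whether change scores are formed or baseline is entered as a level of time.

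The baseline score is scheduled. At the enrolment visit in 6.3.1 the staff are to do the following: "Obtain participant's responses on VAS, ODI, EQ-5D, SF-36, and Press Ganey Patient Satisfaction Scale". The schedule of events lists VAS, EQ-5D, ODI and SF-36 at baseline and at 6 weeks, 3, 6 and 12 months. The only stated statistical use of baseline data is descriptive (9.3.3): "Descriptive statistics of all participants enrolled will be generated, including demographics and clinical diagnosis characteristics at baseline".

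On size and allocation, 5.3 says "20 participants will be recruited for this study", and 9.4.1 says "Study participants will be assigned to study groups by permuted block random assignment at the enrollment visit". No stratification and no allocation ratio are given.

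**The concern.** Subtracting the baseline score assumes that a participant who starts one point higher stays one point higher at follow-up. Baseline and follow-up scores are normally correlated below 1, so this over-corrects: an arm that happens to start worse tends to show more improvement even if the devices are identical. In a trial of 20, sizeable chance differences at baseline are common, and a reader cannot separate that part of a device difference from a real one.

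The noise in the baseline measurement also enters every improvement score in full. A regression on baseline takes out only the part that predicts follow-up. Using the baseline score by subtraction alone therefore usually gives a wider interval for the device difference on VAS, ODI, EQ-5D and SF-36 than the same data could support.

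**Working it through.** **Inputs.** From the protocol: 20 participants (5.3), one baseline and four follow-up measurements (6.3), and a comparison of improvement between groups (9.3.2). Assumed: 1:1 allocation, so 10 per arm; equal SDs, with everything in SD units; and one common correlation ρ between any two visits, varied from 0.3 to 0.9. The protocol gives no power, effect size, SD or correlation, so there is no figure of its own to reproduce.

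**Step 1: chance imbalance.** The standard error of the baseline difference is √(2/10) = 0.447 SD. The probability of a gap above 0.5 SD in either direction is 2 × [1 − Φ(0.5/0.447)] = 26%.

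**Step 2: how much reaches the device estimate.** Given a baseline difference D, the expected follow-up difference with no device effect is ρD, so the expected difference in change is ρD − D = −(1 − ρ)D. For D of one standard error:

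- ρ = 0.3: 0.7 × 0.447 = 0.31 SD
- ρ = 0.5: 0.5 × 0.447 = 0.22 SD
- ρ = 0.7: 0.3 × 0.447 = 0.13 SD

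A simulation of 20,000 trials per setting, on the mean of the four visits, gave slopes of −0.71, −0.50 and −0.30 for the change score. With baseline as a covariate the slopes were within about 0.01 of zero.

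**Step 3: precision.** For the mean of four follow-up visits, variance per participant:

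- change score: (1 + 3ρ)/4 + 1 − 2ρ = 1.25(1 − ρ)
- baseline-adjusted: (1 + 3ρ)/4 − ρ²
- ratio, adjusted to change: (1 + 4ρ)/5

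Estimating the slope with 20 participants multiplies the adjusted variance by about 1 + 1/(20 − 4) = 1.0625. For a single visit the ratio is (1 − ρ²)/[2(1 − ρ)] = (1 + ρ)/2, with the same multiplier.

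| ρ | Four-visit mean | Single visit |
|---|---|---|
| 0.3 | 0.440 × 1.0625 = 0.47 | 0.65 × 1.0625 = 0.69 |
| 0.5 | 0.600 × 1.0625 = 0.64 | 0.75 × 1.0625 = 0.80 |
| 0.7 | 0.760 × 1.0625 = 0.81 | 0.85 × 1.0625 = 0.90 |
| 0.9 | 0.920 × 1.0625 = 0.98 | 0.95 × 1.0625 = 1.01 |

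The result depends on the correlation structure. If follow-up visits correlate r with each other and ρ with baseline, the four-visit ratio is [(1 + 3r)/4 − ρ²] / [(1 + 3r)/4 + 1 − 2ρ]. With r = 0.6 and ρ = 0.3 it is 0.61/1.10 = 0.555, or 0.59 after the multiplier. With r = 0.8 and ρ = 0.5 it is 0.60/0.85 = 0.706, or 0.75.

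**Step 4: error rate and power.** These come from the same simulation, with a two-sided 5% test on the four-visit mean.

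- No device effect, all trials: both analyses rejected in 4.8% to 5.3%.
- No device effect, only trials with a baseline gap above 0.5 SD: the change score rejected in 15%, 12% and 10% at ρ = 0.3, 0.5 and 0.7, against 5% to 6% with the covariate.
- Assumed device effect of 0.8 SD: power rose from 43.9% to 75.1%, from 57.4% to 76.4%, and from 78.5% to 86.5%.

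**Step 5: the other reading of 9.3.2.** If baseline is a fifth level of time, each visit-versus-baseline contrast between devices is again a difference in change, so steps 2 and 3 apply to it. The main effect of device would average four levels that the device can affect with one that it cannot, so a constant effect d would appear as 4d/5. Neither reading amounts to baseline adjustment.

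**The case against.** The strongest reply is that 9.1 calls section 9 a general outline and promises a detailed SAP before analysis. Covariates are commonly settled there, and 9.3.2 does not forbid one. That is fair as far as it goes: the protocol is silent on adjustment and does not rule it out. But 9.3.2 does commit to an outcome (improvement) and a model (repeated-measures ANOVA between groups). An SAP that follows it faithfully takes over the less efficient analysis.

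Three stronger readings are tempting, and the documents do not support them.

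- **The baseline score is ignored.** It is not. Improvement already uses it by subtraction; what is absent is baseline as a covariate.
- **The comparison is biased or inflates false positives.** Over all randomisations it does neither. The shift in step 2 is conditional on the imbalance that happens to occur, and the overall 5% error rate already averages over it.
- **A large gain in power is assured.** It depends on a correlation that the protocol does not state, and at about 0.9 nothing is left to gain. For a smaller effect of 0.5 SD, with follow-up correlation 0.6 and baseline correlation 0.3 to 0.5, power goes only from about 17–24% to 26–33%, so the trial is underpowered either way.

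**Conclusion.** The point holds as an avoidable inefficiency, not as an invalid analysis. With no baseline covariate, the device estimate on each questionnaire moves with whatever baseline difference chance produces, by 0.13 to 0.31 SD for a one-standard-error gap at correlations from 0.7 down to 0.3. Its variance is also larger than it need be over that range. At a correlation of 0.9 the two analyses are practically equal, so adjustment loses almost nothing even there.

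The sizes rest on 10 per arm, equal SDs and the assumed correlations. The direction needs only a correlation below about 0.9. The primary fusion endpoint is not touched, and nothing here suggests that the questionnaire results would be wrong on average. The change is worth making because the baseline scores are already scheduled for collection.

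**What to change.** In 9.3.2, replace the ANOVA on improvement with a repeated-measures mixed model for each scale. The outcome is the score at each follow-up visit. The terms are the participant's own baseline score on that scale, device, visit and device-by-visit. Report the baseline-adjusted device difference with its 95% interval. The device-by-visit term also serves the question in 3.2 of which device brings faster improvement. If improvement is preferred as the reported quantity, the change score can be the outcome with the same terms; with the baseline score in the model, the device difference is the same.

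Carry the same model into the SAP, and fix it before any outcome is seen by device, so that adjustment is not chosen after the fact. The cost is a sentence or two of text, one degree of freedom per scale and no new data.

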9.3.3. Baseline Descriptive Statistics

Descriptive statistics of all participants enrolled will be generated, including demographics and clinical diagnosis characteristics at baseline.

9.4. Measures to Minimize Bias

9.4.1. Enrollment/Randomization/Masking Procedures

Study participants will be assigned to study groups by permuted block random assignment at the enrollment visit after a study investigator has determined that the participant meets all inclusion criteria and no exclusion criteria. The study participants will be blinded to which group they have been assigned.

One potential bias that has been identified is the impact of knowing which device one has received on subsequent rating scales. Participants who are aware that they have been implanted with the Tritanium PL Cage may be more inclined to rate their pain as "improved." To ensure participant survey responses are not confounded, participants will blinded to which study group he or she is assigned.

Trial randomization codes will be tracked by the research coordinator by marking the designated section on study participants' enrollment visit CRF. Planned unmasking will occur at the final study visit (12-month visit). Unplanned masking is defined as unmasking that occurs before the final study visit. If a study participant learns to which group he or she was assigned, it will be noted on his or her case report form that masking has been broken. The participant is still permitted to participate in the research study.

Another potential bias that has been identified is the radiologists' interpretation of the CT and X-ray scans. Radiologists who are not informed of the study's hypotheses will perform CT and X-ray evaluation to avoid bias in the interpretation of fusion rate. In addition, two radiologists will independently evaluate the fusion following the guidelines described in this protocol to establish inter-rater reliability.

No dummy techniques will be necessary, as patients will be unable to determine with which device they're implanted. Epic will be utilized to inform other health care providers that the implanted device should not be revealed to the participant.

Study participants who discontinue early (at or before the 6-week study visit) may be replaced if the radiographic imaging was not performed.

9.4.2. Evaluation of Success of Blinding

Participants will be asked at each follow-up visit if he or she has become aware of which device he or she received. The research coordinator will record participants' responses in the CRF.

9.4.3. Breaking the Study Blind/Participant Code

Provide the criteria for breaking the study blind or participant code. Discuss the circumstances in which the blind would be broken for an individual or for all participants (e.g., for SAEs). Indicate to whom the intentional and unintentional breaking of the blind should be reported.

The study blind will be broken when:

- 1. The participant leaves the study for any reason
- 2. A serious adverse event occurs and the Institutional Review Board determines it is necessary for all participants to know device they received

Intentional and unintentional breaking of the blind should be reported in the participant's case report form. If unintentional, a protocol deviation report must be filled out by the PI and submitted to the IRB.

9.4.4. Missing Data

In evaluating primary endpoints, missing radiographic data will be excluded from the analysis. If 6-week radiographic endpoints cannot be obtained, the participant will be removed from the study.

In evaluating secondary endpoints, the following methods will be followed for including missing endpoint values

- Last observation carried forward
- All missing data are worst possible response
- All missing data are best possible response

10. Source Documents and Access to Source Data/Documents

Source data are all information, original records of clinical findings, observations, or other activities in a clinical trial necessary for the reconstruction and evaluation of the trial. Examples of these original documents and data records include, but are not limited to, hospital records, clinical and office charts, laboratory notes, memoranda, participant' memory aids or evaluation checklists, pharmacy dispensing records, recorded audio tapes of counseling sessions, recorded data from automated instruments, copies or transcriptions certified after verification as being accurate and complete, microfiches, photographic negatives, microfilm or magnetic media, x-rays, and participant files and records kept at the pharmacy, at the laboratories, and medico-technical departments involved in the clinical trial. It is acceptable to use CRFs as source documents. If this is the case, it should be stated in this section what data will be collected on CRFs and what data will be collected from other sources.

11. Quality Assurance and Quality Control

The study team will follow SOPs on data entry and storage. Any missing data or data anomalies will be communicated to PI for clarification/resolution.

The study team will follow SOPs on staff training requirements, and a training tracking log will be maintained by the Research Coordinator and stored in the study binder.

Following written SOPs and protocol, the monitors will verify that the clinical trial is conducted and data are generated, documented (recorded), and reported in compliance with the protocol, GCP, and the applicable regulatory requirements (e.g., Good Laboratory Practices (GLP)).

The investigational site will provide direct access to all trial related sites, source data/documents, and reports for the purpose of monitoring and auditing by the sponsor, and inspection by local and regulatory authorities.

12. Ethics/Protection of Human Subjects

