2.3. Potential Risks and Benefits

2.3.1. Known Potential Risks

The potential immediate and long-term risks associated with surgical implantation of the Tritanium PL Cage or PEEK implant are similar to other surgical procedures used to treat spinal instability and deformity. Risks associated with any surgical procedure include:

- Adverse reaction to anesthesia
- Hematoma or seroma at the operative site
- Failure to improve
- Persistent or worsened pain
- Infection of the wound
- Radiation exposure
- Wound dehiscence
- Vascular disorders, including thrombus
- Bronchopulmonary disorders, including emboli
- Genitourinary disorders
- Pneumonia
- Hemorrhage
- Myocardial infarction
- Paralysis
- Death

In addition to the potential risks associated with general surgical procedures, patients who are implanted with the Tritanium PL Cage or PEEK implant may also be at risk for the following:

- Loss of proper spinal curvature, correction, height, and/or reduction
- Delayed union or nonunion

- Neurological and spinal dura mater lesions from surgical traumalnfection or inflammation
- Nerve damage
- Paralysis
- Instrument failure resulting in a complication
- Allergic reaction to implanted materials
- Decrease in bone density due to stress shielding
- Dural leak requiring surgical repair
- Peripheral neuropathies
- Heterotopic bone formation
- Loss of bowel or bladder function

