4.2. Study Endpoints

4.2.1. Primary Endpoint

This study's primary endpoint is time to fusion at post-operative follow-up, evaluated by radiologist interpretation of radiographic and CT imaging.

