9.3. Description of Statistical Methods

9.3.1. Analysis of the Primary Efficacy Endpoint(s)

The primary endpoint analysis involves a comparison of participant fusion rates at 6-weeks, 3-months, 6-months and 12-months after surgical intervention. All participants who were enrolled will be included in this analysis. Participants will be excluded from the analysis if a CT scan and x-ray cannot be obtained at the 6-week visit.

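### The primary fusion analysis excludes missing scans whatever the cause and has no rule for revision, so a failed device can leave the denominator or be counted as fused

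*Protocol*

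**What the plan says.** Protocol section 4.2.1 defines the primary endpoint by imaging alone: "This study's primary endpoint is time to fusion at post-operative follow-up, evaluated by radiologist interpretation of radiographic and CT imaging". Section 9.3.1 gives the analysis: "The primary endpoint analysis involves a comparison of participant fusion rates at 6-weeks, 3-months, 6-months and 12-months after surgical intervention". On the analysis set, the same section says "All participants who were enrolled will be included in this analysis", and then "Participants will be excluded from the analysis if a CT scan and x-ray cannot be obtained at the 6-week visit".

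Section 9.4.4 sets the missing-data rule: "In evaluating primary endpoints, missing radiographic data will be excluded from the analysis". It adds: "If 6-week radiographic endpoints cannot be obtained, the participant will be removed from the study". Section 9.4.1 allows replacement of participants who discontinue by the 6-week visit without imaging. For the secondary endpoints, 9.4.4 names three ways of filling in missing values: last observation carried forward, worst response and best response. For the primary endpoint it names only exclusion.

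Section 4.2.2 lists as a secondary endpoint "Proportion of participants requiring revision/secondary surgical intervention", without limiting it to the treated level or to any reason. Section 2.3.1 lists "Delayed union or nonunion" among the risks of both implants. No section says how a revision enters the fusion endpoint.

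**The concern.** Revision for nonunion or device failure, before fusion has been seen, is strong evidence that the original construct did not fuse. It can also be the reason that later scans are missing, since section 5.4.1 lets the investigator end participation after an adverse event or other medical situation. An exclusion rule that ignores the cause can therefore remove participants because of their outcome. If imaging continues instead, union obtained by the second operation can be read as fusion under the device first assigned.

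Both routes raise the fusion rate of the arm with more such revisions. The stated aim in section 3.1 is to measure the cage's efficacy through the robustness and speed of fusion, and with 20 participants a single reclassified person visibly moves the estimate.

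**Working it through.** **The document trail**

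1. Dropping. Section 9.4.4 excludes missing scans without regard to reason. If the 6-week imaging cannot be obtained, 9.3.1 and 9.4.4 take out the whole participant and 9.4.1 may supply a replacement. After week 6, a missing scan need only remove that visit; earlier readings can stay in their own comparisons.
2. Crediting. Section 6.1.1.5 schedules CT of the treated level(s) at every follow-up visit, with no stop after revision. Section 9.3.1 includes all enrolled. The fusion criteria in Appendix A are imaging findings only. None of these stops a post-revision scan from counting.
3. Correct counting. A revised participant who is scanned and read as not fused is handled properly under the present text.

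**Size, as an illustration**

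The protocol has no figure to reproduce: section 5.3 gives 20 participants without a fusion rate, revision rate, power or effect size. Assumptions: 1:1 allocation, so 10 per arm (section 9.4.1 specifies permuted blocks but no ratio); *f* fused without revision; *r* revised before fusion. The rate for the arm is:

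- counted as not fused: *f*/10
- dropped: *f*/(10 − *r*)
- credited with later union: (*f* + *r*)/10

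| *f* | *r* | Not fused | Dropped | Credited |
|---|---|---|---|---|
| 6 | 1 | 60% | 6/9 = 66.7% | 70% |
| 6 | 2 | 60% | 6/8 = 75.0% | 80% |
| 6 | 3 | 60% | 6/7 = 85.7% | 90% |
| 7 | 1 | 70% | 7/9 = 77.8% | 80% |
| 7 | 2 | 70% | 7/8 = 87.5% | 90% |
| 7 | 3 | 70% | 7/7 = 100% | 100% |
| 8 | 1 | 80% | 8/9 = 88.9% | 90% |
| 8 | 2 | 80% | 8/8 = 100% | 100% |

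Averaged over those revised, the shift from dropping is *f*/[10(10 − *r*)]. It runs from 6/90 = 6.7 points to 7/70 = 8/80 = 10 points. The shift from crediting is 1/10 = 10 points each.

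Now set an arm with *f* = 7 against a second arm with 7/10 fused and no revisions. Counting revision as not fused gives a difference of 0. With 1, 2 or 3 revised, dropping gives +7.8, +17.5 or +30 points, and crediting gives +10, +20 or +30. Fisher's exact test for the largest shifts gives p = 0.23 (7/7 v 7/10) and p = 0.21 (10/10 v 7/10). The effect is on the estimate, not on significance.

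**How likely a revision is**

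The chance of at least one revision among 20 is 1 − (1 − *p*)^20. At assumed risks of 2%, 5%, 10% and 15% this is 33%, 64%, 88% and 96%.

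**The case against.** A reader might infer that the protocol directs post-revision scans to be counted as fusion. It does not. That follows only from reading several sections together in the absence of a rule, and section 9.1 defers detail to a SAP that is not at hand. Silence on revision is therefore not in itself an error. What stands is the written exclusion in 9.4.4: to count a revised participant with missing scans as not fused, a SAP would have to depart from it.

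A reader might also infer that every revised participant is either lost or scored as a success. The text does not support that. Such a participant may be read as not fused. Revision is not named as a reason for withdrawal, and the early termination visit in section 6.3.4 includes CT and X-ray if the participant is willing and it does no harm. That visit does not supply the later scheduled scans, however, and follow-up after withdrawal under 5.4.2 is for safety capture.

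A third tempting reading is that the rules reverse the comparison. A case can be built: 6/10 v 7/10 (−10 points) becomes 6/8 v 7/10 (+5) if two revised participants are dropped, or 8/10 v 7/10 (+10) if they are credited. It needs two revisions for nonunion in one arm and none in the other, and the documents give no rate that makes this likely or unlikely.

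Two further objections stand in part. Revision and nonunion remain visible, as a secondary endpoint and as adverse events, so failure is not hidden; it is only missing from the primary estimate. And a rule that made every reoperation a fusion failure would misclassify in its turn: section 2.3.1 lists haematoma, wound infection and dural leak needing repair, none of which is a nonunion.

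**Conclusion.** The point holds in a limited form. Section 9.4.4 fixes an exclusion that ignores why a scan is missing, sections 9.3.1 and 9.4.1 extend it to removal and possible replacement around week 6, and nothing ties revision to the primary endpoint. Outcome-dependent exclusion, or credit for a second operation, is possible under the text but not certain.

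The size rests on assumed inputs: 10 per arm, 6 to 8 fused without revision, and revisions for nonunion or device failure before fusion. Counting such a revision as not fused is a choice of estimand, not the only defensible one. It suits a question about the device first implanted. It should be settled before results by arm are known, so that the choice cannot follow the result.

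**What to change.** In sections 9.3.1 and 9.4.4, state that:

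- a participant who has revision at a treated level for nonunion or device failure before documented fusion counts as not fused at the first scheduled visit on or after the revision and at every later one;
- that participant stays in the denominator, also when the revision comes before the 6-week imaging, with the replacement sentence in 9.4.1 carrying the same exception;
- in time to fusion, the participant is kept as not fused through 12 months and is not censored at revision, since censoring would assume the same later chance of fusion as in those not revised;
- reoperation for other reasons, for example haematoma, wound infection or dural leak, does not by itself count as fusion failure;
- the exclusion of missing scans applies only to scans missing for other reasons;
- a sensitivity analysis uses observed fusion status regardless of revision.

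The cost is a few sentences and two items on the case report form, the level and the reason for each revision, because 4.2.2 as written requires only that a revision be counted. Assigning the reason takes judgement, and the stated fusion rate may be slightly lower. Clinical care and the imaging schedule do not change.
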